#### Surgical procedures

THR surgery will be performed by anterolateral minimally invasive non-cemented total hip arthroplasty (ALTHA); this approach is currently in routine practice at MMC and there will be no modifications for the purpose of this study.

#### DATA COLLECTION

Demographic and clinical data for each case will be abstracted from the medical record (EPIC) and will include age, gender, height, weight, BMI, total dose of Vecuronium, total dose of Sugammadex, time of surgery, time in the post anesthesia care unit (PACU), and maximum pain score in the PACU. Postoperatively, time to extubation will be tracked (time from the end of surgery to extubation are both points recorded in EPIC) as well as need for intubation, need for mechanical ventilation, need for additional reversal medication, and desaturation. All of these data are recorded through the existing QA database. We will confirm completion of the QA data form for each study patient.

Postoperatively the surgeon will grade the overall surgical conditions using a five point Likert scale (Figure). This scale was based on one published from a study of muscle relaxation in intra-abdominal surgery; it was modified by the Investigator for use in THR, with input from [name]. Satisfaction grading sheets will be collected by the research coordinator at the end of the procedure. The satisfaction ratings will include

patient identifiers to enable research staff to link these data with information abstracted from EPIC.

Figure: Surgical Conditions Rating Scale for THR

1	Extremely poor conditions:	Muscles resistant to retraction and obscure view, implant difficult to insert into socket, requires assist
2	Poor conditions:	Muscles resistant to retraction and obscure view, implant difficult to insert into socket not requiring assist
3	Acceptable conditions:	Muscles resistant to retraction, adequate view, difficult to insert not requiring assist
4	Good conditions:	Muscles relaxed adequate view, Easy to insert
5	Optimal conditions:	Muscles relaxed excellent view, Easy to insert

The surgical condition grading, requests for additional relaxation, time from incision to joint reduction, time to extubation and need for postoperative ventilation will be recorded on a separate data collection sheet (attached). To maintain patient confidentiality, all paper records will be stored in a locked filing cabinet in the research coordinator's office in the Anesthesia Department (card access only) and will be destroyed after data analysis is complete.

All data will be entered into a web-based, HIPAA-compliant REDCap database, to which only the PI and research coordinator have login access. De-identified data will be exported for analysis in Excel or SAS format, as necessary.

#### DATA ANALYSIS

Demographic and clinical data will be summarized using standard descriptive statistics, both for the overall study group and after stratification by NMB group. Continuous data will be shown as mean (standard deviation) or as median (range), as appropriate;

categorical data will be shown as frequency, n (%). Differences between treatment groups will be evaluated first using an intention-to-treat model, with subjects grouped according to the depth of NMB that they were randomized to; in post hoc analysis we will compare data between subjects grouped according to the depth of NMB that they actually received. Categorical data will be compared between groups by chi square test; continuous data will be compared using t tests or their nonparametric equivalent, as appropriate.

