## BACKGROUND

THR is a very common surgical procedure in the US and approximately 600 cases are performed per year at MMC. The hip joint is a ball and socket joint, the head of the femur is the ball and the cup of the pelvic bone is the socket. THR requires an incision through skin and muscle with retraction of the incised muscles to expose the head of the femur which is then removed. The femoral prosthesis is inserted into the femur and next the ball of the femoral prosthesis is then inserted (reduced) into the socket. Thus, tension in the muscles can interfere with their retraction during exposure or with extracting or reducing the femoral head and patients with more developed musculature (males, younger age, physically active) could potentially present a greater challenge to the surgeon.

At MMC general anesthesia utilizing neuromuscular blockade is the routine anesthetic technique. The primary goal of NMB during THR is to facilitate retraction of muscles around the site of surgery to increase the surgeon's view of the operative site during the operation without the need for a longer incision, and to facilitate reinsertion (reduction) of the prosthesis at the end of surgery. Newer minimally invasive hip replacement techniques which use smaller incisions may theoretically require even greater depth of NMB to produce optimal surgical conditions.

Until recently, the depth of NMB during surgery has been limited in practice by the time it takes to reverse the effects and allow adequate return of neuromuscular function for

safe extubation and spontaneous ventilation. The effects of NMB wear off with time; however, this process can be prolonged and in most cases NMB is reversed using medication. Older reversal medications such as Neostigmine act by increasing levels of acetylcholine at the neuromuscular junction, where it competes with the NMB agent for receptor sites. There is however a ceiling effect with this method, which limits rapid reversal of deeper NMB, especially when that deeper NMB is needed near the end of a surgery such as in THR. Thus, the constraints of reversal time limit the depth of NMB that is practical during surgery.

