#### *Sample size*

Sample size calculations, performed using NQuery software (Statistical Solutions Ltd, Boston, MA), were based on a chi square test, comparing the current frequency among surgeries of surgeon requests for additional NMB (estimate, 50%) and an anticipated effect size of 50% (absolute frequency of 25% for requests for additional NMB in the deep NMB group). A sample size of  $n=58/\text{group}$  ( $n=116$  total) would give 80% power to detect this difference at alpha = 0.05. Assuming incomplete data and cancelled surgeries among 10% of patients, we will enroll a total of 128 (64/group). [name] performs ~400 THR surgeries per year at MMC, of which ~280 are among patients aged 50-70 years; thus a minimum enrollment rate of 46% would be required to achieve this sample size over a one year period.

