#### *Randomization*

Patients will be randomized to moderate (Group 1) or deep (Group 2) NMB using a permuted block design (blocks of n=4 and n=6) that is stratified by patient sex. The randomization plan will be developed using NQuery software (Statistical Solutions Ltd, Boston, MA). Sequentially numbered group assignments will be placed in opaque envelopes, with a separate series of envelopes for male and female patients. Immediately before each surgery, the Research Coordinator will retrieve manually the next envelope in sequence from the male or female series, as appropriate, and give this to the anesthesiologist. The surgeon will be blinded to group assignment.

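### Randomisation is stratified by sex but no planned test uses the strata; a sex-stratified analysis could add some power at no cost in patients or data (minor)

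*Combined protocol and SAP*

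**What the plan says.** Under Randomization, patients are allocated "using a permuted block design (blocks of n=4 and n=6) that is stratified by patient sex", with a separate series of envelopes for each sex. Sex is the only stratification factor.

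Data Analysis then sets out the comparisons: "Categorical data will be compared between groups by chi square test; continuous data will be compared using t tests or their nonparametric equivalent, as appropriate". This covers both the intention-to-treat comparison and the later grouping by blockade actually received. The only stratification mentioned there is descriptive, by treatment group. No other section plans a stratified or adjusted test.

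The Sample size section uses the same unadjusted approach: the calculations "were based on a chi square test, comparing the current frequency among surgeries of surgeon requests for additional NMB" with the rate expected under deep blockade.

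Background gives a reason to think sex might matter: "patients with more developed musculature (males, younger age, physically active) could potentially present a greater challenge to the surgeon". It attaches no figure to this. Sex is recorded for every case; the abstracted data "will include age, gender, height, weight, BMI, total dose of Vecuronium", among other items.

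**The concern.** Stratified blocks take chance imbalance between the sexes out of the treatment difference. The unadjusted chi-square and t tests do not know this. Their standard errors still include the variation between men and women, so they are too wide whenever sex predicts the outcome. The tests then reject less often than 5% under the null hypothesis and forgo some power under the alternative.

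Such a link is plausible on the protocol's own account. Males head its list of potentially harder cases, muscle tension is what prompts a request, and resistance of the muscles is part of the surgeon's rating scale. What is at stake is power that the design has already made available. The false-positive rate is not at risk, and the planned power is not undermined, because the trial was sized on the same unadjusted test.

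**Working it through.** **Inputs from the documents.** Moderate arm 50% with a request ("comparing the current frequency among surgeries of surgeon requests for additional NMB (estimate, 50"%), deep arm 25% ("absolute frequency of 25% for requests for additional NMB in the deep NMB group"), 58 per group, which "would give 80% power to detect this difference at alpha = 0.05". Sidedness is not stated; two-sided is taken because it reproduces the plan's figure.

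**Inputs assumed.** The male-female gap in request rates, the share of men, and how the treatment effect divides between the sexes. The documents give none of these.

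**Step 1: the plan's own figure.** With pooled variance under the null and no continuity correction,

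n = [1.960·√(2·0.375·0.625) + 0.842·√(0.5·0.5 + 0.25·0.75)]² / 0.25²

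= (1.342 + 0.557)² / 0.0625 = 57.7, rounded up to 58 per group.

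Power at 58 is 80.2% by this formula and 79.9% by exact enumeration. The stated sample size is reproduced.

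**Step 2: why the unadjusted test is conservative.** Take the null case with a 50% rate in both arms, half men, and a male-female gap g. The chi-square test estimates the variance of the difference as 2·0.25/n. With sex balanced by design, the actual variance is 2·(0.25 − g²/4)/n. The ratio is 1 − g², so the true type I error is about 2·[1 − Φ(1.960/√(1 − g²))]. For g = 0.4 this is 2·[1 − Φ(2.139)] = 3.25%, against 3.30% exactly.

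**Step 3: exact comparison for requests.** All possible outcomes were enumerated with 29 men and 29 women per arm, comparing the uncorrected Pearson chi-square with the uncorrected Cochran-Mantel-Haenszel (CMH) test at two-sided 5%. Moderate-arm rates average 50% and deep-arm rates average 25%. The deep arm has either a common treatment odds ratio or the same sex gap as the moderate arm (constant difference). Type I error uses the moderate-arm rates in both arms.

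| Sex gap (points) | Type I error, chi-square | Type I error, CMH | Power, common odds ratio: chi-square vs CMH | Gain, common odds ratio (points) | Gain, constant difference (points) |
|---|---|---|---|---|---|
| 0 | 5.07% | 5.08% | 79.9 vs 80.0% | 0.1 | 0.1 |
| 10 | 4.96% | 4.98% | 80.0 vs 80.3% | 0.3 | 0.4 |
| 20 | 4.61% | 4.81% | 80.3 vs 81.5% | 1.2 | 1.7 |
| 30 | 4.05% | 4.92% | 80.8 vs 83.6% | 2.8 | 3.7 |
| 40 | 3.30% | 5.13% | 81.5 vs 86.0% | 4.5 | 5.8 |

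With 23 men and 35 women per arm (40% men) the gains at gaps of 10 to 40 points are about 0.3, 1.1 to 1.5, 2.8 to 3.5, and 4.6 to 5.6 points. A separate simulation in terms of sex odds ratios, half male, agrees: 81.1 vs 80.2% at an odds ratio of 2, 83.0 vs 80.7% at 3, and 84.5 vs 81.1% at 4 (CMH first).

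**Step 4: sex gap not carried into the deep arm.** With moderate rates of 65% in men and 35% in women and deep rates of 25% in both, power is 80.5% for chi-square and 81.3% for CMH. With moderate rates of 60% and 40% and deep rates of 15% and 35% (gap reversed), it is 80.4% and 80.5%.

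**Step 5: surgery time.** Assume a treatment effect of 0.525 within-sex SD, which gives about 80% power, and a sex gap of d SD with half men. The t test's error variance is inflated by 1 + d²/4, so its power is about Φ(0.525·√29 − 1.960·√(1 + d²/4)). With 0.525·√29 = 2.827:

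- d = 0 (equivalent to adjusting for sex): 80.7%
- d = 0.3: 80.1%, a loss of 0.6 points
- d = 0.5: 79.0%, a loss of 1.7 points
- d = 0.8: 76.3%, a loss of 4.4 points

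Simulation of the t test against a linear model with sex gives about 0.6, 1.6 to 1.8, and 4.5 to 4.6 points. No figure was computed for the rating.

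**The case against.** Nothing in the plan is invalid. It sizes on a chi-square test and analyses by one, so design and analysis agree, and the unadjusted test after stratified blocks errs only on the cautious side. The gain rests wholly on sex gaps that the documents do not supply. It stays under 2 points until the gap approaches 30 points, which in the moderate arm is already a sex odds ratio of about 3.4 (65% against 35%). The protocol's own rationale is that blockade relieves muscle tension, so deep blockade might shrink the sex gap; the gain then falls to 0.8 points, or 0.1 if the gap reverses (step 4). The rating method has no figures behind it, and the surgery-time figures rest on an assumed effect size. Finally, the first aim speaks of the number of requests, a count, whereas the stratified test applies to the proportion used in the sample size.

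All of this stands as a limit on size, and it is why the point is minor. It does not remove the point. In every pattern tried for requests, the stratified test had at least the power of the unadjusted one, with type I error of 4.8 to 5.1%. How repeated requests in one surgery are counted is a separate question, which needs its own answer.

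**Conclusion.** The concern holds, as a minor efficiency point. Sex is built into the randomisation and left out of every planned comparison. The unadjusted tests remain valid and the sample size is correct for the test it names. If sex predicts requests, the plan forgoes about 0.3 to 0.4 points of power at a 10-point gap, 1.2 to 1.7 at 20, 2.8 to 3.7 at 30 and 4.5 to 5.8 at 40, and its type I error drifts down to 3.3% at the largest gap. These figures assume half men, 58 per group, and a sex gap that persists under deep blockade; if it does not persist, the gain is below 1 point in the cases tried. If sex is unrelated to requests, the two tests perform alike. The textual mismatch is certain; the practical benefit is unknown because the documents give no outcome by sex.

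**What to change.** Add a short paragraph to Data Analysis, fixed before any outcome is compared by group:

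- Proportion of surgeries with a request: CMH test stratified by sex, with the Mantel-Haenszel risk difference and its 95% confidence interval.
- Surgeon's rating: van Elteren test, that is, a rank test stratified by sex.
- Time from incision to joint reduction: linear model with treatment and sex.
- Unadjusted chi-square, t or rank tests: kept as sensitivity analyses.

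The cost is the paragraph itself. No patients, data or procedures are added, since sex is already recorded and is known at randomisation. The sample size need not change. Naming the methods in advance also prevents a choice between adjusted and unadjusted results once they have been seen.

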#### SPECIFIC AIMS

- 1) Assess difference in surgical conditions between moderate and deep NMB groups.  
Enrolled patients will be randomized to receive moderate (n=58) or deep (n=58) NMB. Difference in surgical conditions will be evaluated by:
  - a) The number of requests from the surgeon for additional relaxation (NMB) during the procedure. At any time during the operation if the surgeon feels the muscle tension is interfering with ease of operation he will ask for additional muscle relaxation. If the patient is moderately relaxed they will be converted to deep relaxation with additional muscle relaxants. If they are already deeply relaxed no additional relaxants will be administered (as is our current practice). All requests will be recorded.
  - b) Rating by the surgeon after each surgery using an internally developed satisfaction scale. The scale was developed by modifying a scale used in a previous study of muscle relaxation in intra-abdominal surgery to specify two key elements identified by our surgeon: ease of muscle retraction and femur manipulation.

- 2) Assess the impact of deep vs moderate NMB on time of surgery, measured from the time of incision to joint reduction.

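### No ordinal method is assigned to the five-grade surgical rating, and the plan's literal rule, chi-square, ignores the order of the grades

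*Combined protocol and SAP*

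**What the plan says.** Specific Aims lists two measures of surgical conditions: the surgeon's requests for more relaxation, and a rating after each operation. Under Data Collection, "the surgeon will grade the overall surgical conditions using a five point Likert scale", running from 1 (worst) to 5 (best), each grade with a verbal description.

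The Data Analysis section gives two general rules. The first is that "Categorical data will be compared between groups by chi square test". The second gives continuous data a t test or a nonparametric counterpart. The rating is not mentioned, is not placed in either class, and no method for ordered categories is named.

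Randomization uses a permuted block design "that is stratified by patient sex"; the Data Analysis section makes no use of sex.

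The only power statement concerns requests. The Sample size calculations "were based on a chi square test, comparing the current frequency among surgeries" with the anticipated deep-group rate. No distribution, effect size or power is given for the rating.

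**The concern.** The hypothesis at the end of Background is directional: deeper block should improve conditions. A Pearson chi-square test on the 2x5 table gives the same p-value however the five columns are arranged. It spends 4 degrees of freedom on any kind of difference, so it can miss a steady movement toward better grades. It also returns no direction and no effect estimate, although the Significance section says that better conditions would change routine practice.

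The lenient reading has its own cost. If the 1-to-5 score may be treated as continuous, then chi-square, t test and rank-sum test are all open for an Aim 1 measure, and the choice could be made after the data are seen. Either reading calls for the test to be named in advance.

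Background also suggests that male patients, as one of the groups with more developed musculature, may be harder to operate on. Sex is therefore plausibly prognostic for the rating as well as being the randomisation stratum.

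**Working it through.** **Step 1: the plan's own figure.** Inputs from Sample size: request rates of 50% (moderate) and 25% (deep), 80% power, alpha 0.05. Sidedness is not stated; two-sided is assumed. With pooled variance and no continuity correction:

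n = [1.960 × √(2 × 0.375 × 0.625) + 0.842 × √(0.50 × 0.50 + 0.25 × 0.75)]² / 0.25²

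= (1.342 + 0.557)² / 0.0625 ≈ 57.7, so 58 per group.

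Power at 58 is 80.2%. The stated size reproduces (one-sided would give 46, a continuity correction 66). It concerns requests, not the rating.

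**Step 2: assumptions for the rating.** The documents supply only the scale, 58 per group and alpha 0.05. The rest is assumed: eight moderate-arm grade distributions (seven using all five grades, one with grade 1 almost empty) and a common odds ratio (OR) for better grades. For example, 5/15/30/30/20% has cumulative odds of 0.0526, 0.25, 1 and 4. Dividing by OR 2 and converting back gives 2.6/8.5/22.2/33.3/33.3% in the deep arm.

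**Step 3: simulation.** 20,000 trials per scenario, two-sided 5%. Pearson chi-square (empty grades dropped) is compared with the tie-corrected, unstratified Wilcoxon rank-sum test. Ranges are over the seven five-grade distributions.

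| Assumed OR | Chi-square power | Rank-sum power | Deficit (points) | Deficit, grade 1 almost unused |
|---|---|---|---|---|
| 1.5 | 11–14% | 21–23% | 10–11 | 8 |
| 2 | 30–34% | 50–55% | 20–22 | 16 |
| 2.5 | 51–57% | 72–78% | 21–23 | 17 |
| 3 | 69–74% | 86–91% | 17–18 | 13 |
| 4 | 87–93% | 96–99% | 6–9 | 5 |

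With no effect, chi-square rejects in 3.8 to 5.1% of trials and rank-sum in 4.8 to 5.1%.

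**Step 4: analytic check.** At noncentrality 7.849, a 1-df test has 80.0% power and a 4-df test 59.5%, a gap of 20.5 points.

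**Step 5: effects without a common odds ratio.**

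| Assumed effect | Chi-square | Rank-sum |
|---|---|---|
| Grades 1–3 together fall from 50% to 25%, proportions otherwise kept | 59% | 69% |
| Uneven shift spread over the grades | 72.5% | 85.5% |
| Movement only from grade 4 to 5 | 61% | 21% |
| Movement only from grade 3 to 4 | 80% | 36% |
| Movement from the middle to both ends | 86% | 62% |

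The first two keep the advantage of the rank test, at 10 and 13 points. The last three reverse it.

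**The case against.** The strongest reply is that the plan does not choose chi-square for the rating. The Data Analysis section never classifies it, the scale is scored 1 to 5, and the same sentence permits nonparametric tests where appropriate, so an analyst could use a rank-sum test without departing from the text. This stands in part: chi-square is the literal reading, not a stated commitment. But the nonparametric clause is attached to continuous data, so the rank test is only possible, not assigned.

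Second, the power deficit rests wholly on assumed inputs, and a uniform shift cannot be taken for granted. Moderate-arm patients are moved to deep block when the surgeon asks, requests are expected in about half of current cases, and the grade is given afterwards. Conversion could dilute the contrast or bend it unevenly across grades. This stands, and it is why the figures are conditional.

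Third, a reader might infer that sparse low grades make chi-square invalid. The documents do not support that, because they give no expected distribution. In the 5/15/30/30/20% example at OR 2, expected counts per arm are 58 × (0.05 + 0.026)/2 ≈ 2.2 in grade 1 and 58 × (0.15 + 0.085)/2 ≈ 6.8 in grade 2, so only grade 1 falls below 5. The simulated error rate was not inflated.

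Fourth, if the rating is categorical, the plan already reports n (%) by arm. That would show direction, but it gives no estimate or interval.

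Fifth, sex stratification bears on every outcome, and a plain rank-sum test would cure the main defect. This is fair; no gain from stratifying was calculated here.

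**Conclusion.** The point holds in a conditional form. An ordered Aim 1 measure has no assigned ordinal analysis, and the literal rule sends it to a test that ignores order. With 58 per group and an assumed common odds ratio of 2 to 3, the cost is about 17 to 23 points of power with all five grades in use and 13 to 17 with grade 1 almost unused. At 1.5 or 4 it is about 5 to 11 points.

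Three stronger readings are tempting and unsupported. One is that the plan has committed to the wrong test; it has not named one. Another is that a fixed amount of power is lost; no input for that figure is in the documents, and chi-square gains if the effect is confined to two adjacent grades or runs to both ends. The third is that the trial is mis-sized; it is sized on requests, and chi-square suits requests compared as a yes/no frequency.

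The change should be made, but the main sizing of the trial does not depend on it.

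**What to change.** Add to the Data Analysis section that the 1-to-5 rating will be compared between randomised groups by a Wilcoxon rank-sum test stratified by sex (van Elteren). The effect estimate would be a common odds ratio with 95% confidence interval from a proportional-odds model that includes sex. State that n (%) in each grade will be shown by arm.

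The cost is one or two sentences: no new data, no change to the 58 per group, and no change to the chi-square test for the frequency of requests. The small downside is less sensitivity to differences that are not a consistent shift across the grades, including an improvement confined to one pair of adjacent grades. The table of grades by arm would still show these.
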